3. Medical conditions for which death is likely within 6 months
4. Does not have capacity to consent for the project or participate in survey interview
5. Diagnosis of dementia
6. Patient has no phone or incapable of using text messages
7. Patient has opted out of participating in research noted within MGB Epic EHR system
8. Patient is on enhanced respiratory, airborne or contact plus precautions

4.1b Network subjects:

Inclusion Criteria:

Those people 18 years of age or older identified by patient-subjects randomized to the intervention (social network) arm during completion of the validated PERSNET instrument will be included.

Exclusion Criteria:

1. Participants who do not meet the defined inclusion criteria
2. Participant has no phone or are incapable of using text messages
3. Does not agree to participate

4.1c Exclusion of non-English speaking participants

We plan to exclude patient- and network-subjects who do not speak basic English, as the counseling component of the pilot intervention program and study-related text messages will be in English and the program does not have the ability to translate any non-English inputs. We plan to expand the language ability of the program, pending the success of this pilot program.

4.2 RECRUITMENT PROCEDURES:

4.2a Patient subjects

Similar to IRB approved study ([name], 2020P003739), the Research Assistants (RA) or other study staff will perform daily EHR screening of Brigham and Women's Hospital, Massachusetts General Hospital and Spaulding Rehabilitation Hospital inpatient admissions based on the study's inclusion and exclusion criteria listed above. If an inpatient meets criteria, study staff will inform the primary neurologist and nursing staff of a potential patient participant on their service and request their approval for the patient to be contacted for research purposes. Study staff will then request the patient's nurse to introduce the study to the patient and obtain the patient's permission to be contacted by study staff during their inpatient stay. Once permission has been obtained by both the nursing staff and patient, the study staff will approach the patient.

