5.1 PATIENT SUBJECT ENROLLMENT

The study staff will perform daily screening of hospital admissions based on the study’s inclusion and exclusion criteria listed above. If an inpatient meets criteria, the study staff will directly approach the nurse, physician attending, or physician assistant who is caring for the patient to briefly explain the study and determine an appropriate time to meet with the patient. We will verify the inclusion and exclusion criteria with the treating provider. If permission is granted by the treating provider, the study staff will meet with the patient at bedside, explain the study to the patient, and ask the remaining exclusion criteria to confirm their eligibility. In particular, the study staff will confirm that the patient has a phone and is capable of sending and receiving text messages. Study staff will also ensure that patients are willing to engage network members in the study if assigned to the intervention arm. If the patient is interested in participating in the study, the study staff will then obtain informed consent from the patient using MGB-approved REDCap digital signature consent process, conduct baseline surveys, randomize the patient and, for intervention arm participants, collect contact information for their network members who will be directly contacted and invited to participate. Patients will be stratified according to network size (<5 vs 5 or more) and location of hospitalization (MGH or BWH), and then be randomized using a 1:1 ratio to receive individual hypertension counseling or the social network intervention.

Patients who are eligible for participation in this study and two other IRB approved studies led by [name] ([name], 2020P003739 and 2020P000320) may be approached for participation in both studies within one enrollment visit. Study staff will explain both studies and emphasize that patients can choose to only participate in one of the studies. If interested, patients will be provided consent forms for both studies and will agree to participate in each study separately. Patients will then go through baseline questionnaires for both studies, completing any repeated questionnaires between both studies only once. Participation in the three studies will otherwise be separate.

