6. STUDY PROCEDURES

6.1 Consent/Enrollment and Baseline Visit

The study staff will meet with the eligible patients at bedside, explain the study to the patient, and obtain written informed consent using MGB-approved REDCap digital signature consent process. The consent form will include consent for enrolled participants to receive follow-up outreach after

completion of the trial to participate in an implementation evaluation, to include either a brief survey or a brief qualitative interview. Study staff will then help the patient complete baseline questionnaires consisting of the validated PERSNET social networks questionnaire, stroke information, and the CES-D depression screen. Additional covariates, such as medication use, will be retrieved from the EHR. The PERSNET resulting network map will be used to identify network team members. Participants will then be randomized to either the Social Networks (intervention) arm or the Individual Counseling (control) arm. In the Individual Counseling arm, while the patient's network will be mapped, it will not be acted upon. In the Social Network arm, network members identified will be invited to participate in the study per the enrollment description above (Section 5.2). All patients will be provided with a wide-range blood pressure cuff (Medline MDS4001 blood pressure monitor) and instructions for weekly home monitoring. Patient will be asked to use this cuff to collect a baseline blood pressure measurement at the time of enrollment. A blood pressure measurement will also be collected from the patient's EHR on the day of discharge from the hospital. Finally, patients will be offered several Zoom meeting options and will schedule the first counseling session with study staff based on their availability.

Both this study and protocols 2020P003739 and 2020P000320 ask patients to complete the PERSNET social networks questionnaire. To simplify the enrollment process, patients that have consented to participate in both studies will only be asked to complete these questionnaires once for protocol 2022P000444. Data from these questionnaires will then be shared with protocols 2020P003739 and 2020P000320.

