6.3 Counseling Sessions

All counseling sessions will take place remotely through Zoom, an MGB-approved secure video platform. In both the individual counseling and social network arm, participants will meet with the study nurse with an RA present on weeks 2,6, and 12 (+/- 7 days).

6.3a Counseling Session 1—On Week 2 (+/- 7 days)

The first counseling session will take place two weeks after initial enrollment. Study staff will ensure that only participants who have completed the consent process join the Zoom meeting.

Individual Counseling Arm

Patients in the individual counseling arm will meet individually with the study nurse. The nurse will provide counseling on the basics of blood pressure, taking and adjusting medications, monitoring blood pressure, reducing salt, and being physically active. The patients will then schedule their next session and collect a blood pressure measurement with cuff provided by the study staff under direct supervision by the nurse.

Social Network Arm

At the beginning of this session, the Research Assistant/study staff will confirm that all network-participants have completed the electronic consent process via REDCap.

The study nurse will begin the team-based counseling session in which she will provide counseling on teamwork and the same blood pressure control topics covered with the individual counseling group. The teamwork specific topics will include how networks can work together as a team, communication tips for engaging with one another and spreading positive messages and establishing the roles and responsibilities of each network team member. The team will schedule the following session and the patient will collect a blood pressure measurement with the cuff provided by the study staff under direct supervision by the nurse.

6.3b Counseling Session 2—On Week 6 (+/- 7 days)

The second counseling session will take place six weeks after initial enrollment. Participants in both arms will have received text messages every week in the three weeks between session 1 and session 2. Study staff will ensure that only participants who have completed the consent process join the Zoom meeting.

Individual Counseling Arm

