6.4 End line Study Session—On Week 12 (+/- 7 days)

The third counseling session will take place twelve weeks after initial enrollment. Participants in both arms will have received text messages every week in the five weeks between sessions 2 and 3. Study staff will ensure that only participants who have completed the consent process join the Zoom meeting.

Individual Counseling Arm

Patients in the individual counseling arm will meet for a final time with the study nurse. In this session, the patient will check their blood pressure under direct video observation by the nurse. The nurse will also assess the study's secondary outcomes by taking note of the patient's blood pressure in relation to post-stroke hypertension treatment goal of <130/80 and the patient-reported physical function (based on the NIH PROMIS physical function sub-scale). Participants' social networks will be mapped to assess changes that may have occurred as a result of this study.

Social Network Arm

Patients in the social network arm will meet with their network team and the study nurse for a final time. In this session, the study nurse will first conduct a semi-structured interview with the patient and network members to assess the process and effectiveness of the sessions, as well as their views on their teamwork over the course of the intervention (see "*Interview Guide*" attachment). Prior to the interviews, subjects will be asked to provide verbal consent for audio recording of the interview. Patients will not be forced to participate and may withdraw their consent to participate at any time. Participants will be informed that participation is voluntary and that the interviews are part of the research study. The semi-structured interviews after the will be audio recorded, transcribed by the study team or by Landmark Associates (with whom MGB has a BAA agreement) and analyzed using qualitative software to identify themes using a grounded theory approach.

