All network members will then be asked to leave the Zoom meeting, except for the primary caregiver (if applicable). The patient will collect a final blood pressure measurement under direct supervision of the study nurse, complete the PROMIS physical function scale, and remap their network with the PERSNET instrument to assess any changes that may have occurred as a result of the study. The primary caregiver network member will be asked to complete the caregiver burden scale which will be sent to them via a link in the Zoom chat or via text message.

Outcomes

The primary outcome of the study will be absolute reduction in systolic blood pressure at 3 months. Secondary outcomes will be attainment of a post-stroke hypertension treatment goal and patient-reported physical function. Feasibility measures will also be assessed throughout the intervention. End line caregiver burden will be measured in the social network arm compared to historical control data.

The intervention process evaluation conducted using semi-structured qualitative interviewing during the final session (Social Networks arm) will be analyzed using qualitative software to identify themes using a grounded theory approach. Once the data are analyzed, the investigators will review the findings to consolidate observations into a common set of themes.

Finally, a shortened version of the validated PERSNET utilizing only a subset of the initial questionnaire will be tested for predictive accuracy against the results of the full validated PERSNET scale.

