9.3 Statistical analysis

The primary outcome will be absolute reduction in systolic blood pressure at 3 months. Secondary outcomes will be attainment of a post-stroke hypertension treatment goal of <130/80 and patient-reported physical function (based on the NIH PROMIS physical function sub-scale). These outcomes will be evaluated, for intervention and control patients, on a 10-minute Zoom exit interview with direct observation on video by the study nurse.

Analysis will be conducted using intention-to-treat principles. Evaluation of the primary outcome and physical function secondary outcome will be completed using linear controlling for any differences in baseline variables despite randomization. Logistic regression will be used for attainment of post-stroke hypertension treatment goal of <130/80 controlling for any differences in baseline variables.

For Aim 2, we will assess how a subset of questions in PERSNET predict the set of network members who were engaged in the intervention. We will calculate positive predictive value of the subset questions versus full network survey questions.

10. Monitoring and Quality Assurance

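### Eligibility checks only for a phone and texting, but all sessions and the week-12 primary blood pressure reading need video, so patients whose primary outcome cannot be measured as planned can be randomised

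*Combined protocol and SAP*

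**What the plan says.** **Screening.** Section 4.1a, exclusion 6, reads "Patient has no phone or incapable of using text messages". Section 5.1 turns this into a bedside task: "the study staff will confirm that the patient has a phone and is capable of sending and receiving text messages". Neither place mentions video, an internet connection or Zoom.

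**Delivery.** Section 6.3 states: "All counseling sessions will take place remotely through Zoom, an MGB-approved secure video platform". This covers weeks 2, 6 and 12 in both arms.

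**Outcome.** Section 9.3 says the primary and secondary outcomes are evaluated in both arms "on a 10-minute Zoom exit interview with direct observation on video by the study nurse". Section 6.4 agrees. In the control arm, "the patient will check their blood pressure under direct video observation by the nurse". In the network arm, within the same Zoom session, "The patient will collect a final blood pressure measurement under direct supervision of the study nurse".

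**Equipment and set-up.** Section 6.1 says "All patients will be provided with a wide-range blood pressure cuff" and names no other device. Zoom first arises for the patient as a scheduling step, listed after randomisation: "patients will be offered several Zoom meeting options and will schedule the first counseling session with study staff based on their availability".

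**The concern.** The criterion tests the channel that carries reminders and tips. It does not test the channel that delivers both arms and measures the endpoint. Being able to text does not imply a camera, a data connection or the use of someone else's device.

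A patient who lacks all of these passes screening, is randomised, and then can neither attend a session as described nor give the observed reading at week 12. Under the intention-to-treat analysis in section 9.3, that patient is a missing primary outcome that could have been foreseen at the bedside. Section 9.3 states no missing-data method, so the plan does not say how such a patient would be handled. The stake is avoidable loss in a trial of 60 with little slack.

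**Working it through.** **1. Is there a rescue in the text?** The possible candidates are these:
- The health-record blood pressure in section 6.1 is taken on the day of discharge, not at week 12.
- Weekly home monitoring (6.1) is not named as a source for any outcome.
- Email (6.2) is back-up contact only.
- The tablet mentioned in section 7 appears in a data-security statement and is not described as a loan to patients.
- Connection problems (Data Collection Schedule) are recorded as a feasibility measure, with no action attached.

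None supplies a week-12 reading for a patient without video. The baseline reading is taken in hospital and is not affected.

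**2. Reproduce the plan's sample size.** Inputs from section 9.2 are a difference of 10 mm Hg, SD 13, alpha 0.05 and power 0.80. Sidedness is not stated; two-sided is taken here because it reproduces the plan's figure.

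n per arm = 2 × SD² × (1.960 + 0.842)² / difference² = 2 × 169 × 7.85 / 100 = 26.5, rounded up to 27, or 54 in total. This matches the plan. A two-sided t-test gives 28 per arm (56 in total), and a one-sided normal calculation gives 21 per arm.

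**3. Implied allowance.** 60 − 54 = 6 patients, and 6/60 = 10%, for loss from every cause.

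**4. Effect of lost readings.** The documents give no share of patients without video, so the shares below are assumptions. Each also assumes that every such patient yields no outcome and that losses are equal in the two arms.

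Power = Φ(10 / (13 × √(2/n)) − 1.960), where n is the evaluable number per arm. For n = 24: 13 × √(2/24) = 3.753; 10/3.753 = 2.665; 2.665 − 1.960 = 0.705; Φ = 0.760.

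| Assumed share lost | Lost of 60 | Evaluable per arm | Power, normal approximation | Power, t-test |
|---|---|---|---|---|
| 0% | 0 | 30 | 0.846 | 0.834 |
| 5% | 3 | 28.5 | 0.827 | 0.814 |
| 10% | 6 | 27 | 0.807 | 0.792 |
| 20% | 12 | 24 | 0.760 | 0.742 |

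If a 10% loss from lack of video came on top of a 10% ordinary loss (also an assumption), 60 × 0.9 × 0.9 = 48.6 patients would be evaluable. Power would be 0.765 (t-test 0.747).

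**5. Can recruitment absorb a narrower criterion?** Section 9.2 expects 1126 eligible patients × 20% = 225 willing, about 19 per month. If 20% of them were excluded, 225 × 0.8 = 180 would remain for 60 places. The monthly figure would be 19 × 0.8 = 15.2, so 60 places would take 60/15.2 = 3.9 months. That is within the plan's own 4 to 5 months.

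**The case against.** **This is a pilot with deliberately broad entry.** Section 9.2 relies on broad criteria, connection problems are a prespecified feasibility measure, Aim 3 studies acceptability, and section 6.5 follows up patients who withdraw. Screening out patients without video removes some of what the pilot might learn. This stands in part, and counting those excluded answers it. It does not remove the point: the trial is also powered for a between-arm difference, and recording a failed connection does not recover a reading. Section 4.1c already excludes patients who could not follow the counselling because of language, so inability to receive the intervention is an accepted ground for exclusion.

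**A basic phone is not the same as no video access.** This stands. Nothing requires Zoom to run on the patient's own phone. A reader might infer that every patient whose phone lacks a camera is lost. The documents do not support that; the group at risk is patients with no usable device from any source.

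**Access problems may surface informally.** The study is explained before consent, and Zoom times are arranged at the baseline visit. The consent pages and the protocol's attachments are not in the public text and may mention video. This is possible, but section 6.1 lists scheduling after randomisation, and section 5.1 spells out the check without video.

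**Differential loss.** A reader might infer that controls would be lost more often, because network-arm patients have helpers on the call. The documents do not support a direction. Network members join remotely and, under section 5.2, may be anywhere in the United States. A control patient's household is free to help. Network sessions also need more people to connect, which could cut the other way.

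**Screening does not prevent later failure.** This stands. A connection that fails after discharge would need a named substitute reading and a missing-data method, which the plan also lacks.

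**Conclusion.** The mismatch is plain in the text: eligibility requires texting, while delivery and the primary measurement in both arms require video. Following the stated rule can randomise patients whose primary outcome cannot be obtained as planned.

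The size of the problem is unknown. On the plan's own approximation, power stays at or above 0.80 for losses up to 10%. At 10%, however, lack of video alone uses the whole allowance of 6. Power falls below target at the assumed 20%, or when 10% is added to 10% ordinary loss. These figures rest on assumed shares and on every affected patient giving no reading.

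A reader might conclude that the sample size is wrong or that the trial is underpowered. Neither follows, since 54 reproduces and no loss rate is documented. This is a cheap improvement worth making, with high confidence in the gap and low confidence in its effect.

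**What to change.** In section 4.1a, extend exclusion 6 to patients who will have no access after discharge, on their own device or that of a household member or helper, to a device and connection that can join a Zoom video call.

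In section 5.1, have staff confirm this before randomisation, alongside the phone and text check, by asking which device and connection will be used at home. A test call from the ward is not enough, because it shows the hospital connection and not the home one.

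Record the number excluded for this reason and report it with the feasibility measures.

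The cost is one line in each of two sections and a few minutes at the bedside. The downside is a slightly narrower population, limited to patients who could receive neither arm as written, and the expected pool covers this.

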5.1 PATIENT SUBJECT ENROLLMENT

The study staff will perform daily screening of hospital admissions based on the study’s inclusion and exclusion criteria listed above. If an inpatient meets criteria, the study staff will directly approach the nurse, physician attending, or physician assistant who is caring for the patient to briefly explain the study and determine an appropriate time to meet with the patient. We will verify the inclusion and exclusion criteria with the treating provider. If permission is granted by the treating provider, the study staff will meet with the patient at bedside, explain the study to the patient, and ask the remaining exclusion criteria to confirm their eligibility. In particular, the study staff will confirm that the patient has a phone and is capable of sending and receiving text messages. Study staff will also ensure that patients are willing to engage network members in the study if assigned to the intervention arm. If the patient is interested in participating in the study, the study staff will then obtain informed consent from the patient using MGB-approved REDCap digital signature consent process, conduct baseline surveys, randomize the patient and, for intervention arm participants, collect contact information for their network members who will be directly contacted and invited to participate. Patients will be stratified according to network size (<5 vs 5 or more) and location of hospitalization (MGH or BWH), and then be randomized using a 1:1 ratio to receive individual hypertension counseling or the social network intervention.

Patients who are eligible for participation in this study and two other IRB approved studies led by [name] ([name], 2020P003739 and 2020P000320) may be approached for participation in both studies within one enrollment visit. Study staff will explain both studies and emphasize that patients can choose to only participate in one of the studies. If interested, patients will be provided consent forms for both studies and will agree to participate in each study separately. Patients will then go through baseline questionnaires for both studies, completing any repeated questionnaires between both studies only once. Participation in the three studies will otherwise be separate.

Patient subjects will indicate their preference for how they receive a copy of their signed consent form during the consent process. Participants will be able to choose to receive the signed consent through email, mail or receive a hard copy while in the hospital. If they prefer to receive the consent through email or mail, they will provide the address to send the consent form to.

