The study will enroll 60 patients hospitalized at Brigham and Women's Hospital, Massachusetts General Hospital and Spaulding Rehabilitation Hospital with a symptomatic and imaging-confirmed ischemic stroke and hypertension. During the index stroke admission, all enrolled patients' networks will be mapped using the validated PERSNET instrument.¹¹ Participants will then be stratified according to network size (<5 vs 5 or more) and location of hospitalization (MGH or BWH). Network size is the most potent network metric related to stroke recovery.⁹ Patients in both arms will be administered blood pressure medications as needed during the hospitalization. Patients will then be randomized to receive individual hypertension counseling (control) or the social network intervention. In the individual hypertension counseling arm, patient networks will not be acted upon. The index patient will meet via Zoom three times over the course of 3 months with a clinical research nurse for blood pressure education. In the social network arm, the results of the PERSNET instrument will be used to identify the most influential network members based on their network position, driving distance from the patient, speaking frequency, and whether they have high blood pressure. Network members will then be contacted and consented for participation in the study. The index patient and consented network members will meet via Zoom for three visits over 3 months with a clinical research nurse for blood pressure education and teamwork coaching. The primary outcome of the study will be the absolute reduction in systolic blood pressure at 3 months follow-up.

3.1 Study Schema:

Screen potential participants hospitalized at MGB by inclusion and exclusion criteria Total N: 60 patients

4. Subject Selection

4.1 INCLUSION/EXCLUSION CRITERIA:

4.1a Patient subjects

The study team will enroll 60 patients hospitalized at Brigham and Women's Hospital, Massachusetts General Hospital and Spaulding Rehabilitation Hospital with a symptomatic and imaging-confirmed ischemic stroke and hypertension.

Inclusion Criteria:

1. Acute ischemic stroke defined clinically with support from imaging if necessary
2. 21 years of age or older
3. History of hypertension or has been newly prescribed blood pressure medications during index admission
4. Within 14 days after stroke

Exclusion Criteria:

1. NIHSS > 21
2. Significant aphasia (Score>1 on the language section of the NIHSS)

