9.2 Power analysis

This pilot trial will be conducted for 12 months. In that time frame, the study team expects 1126 patients to be eligible across Brigham and Women's Hospital, Massachusetts General Hospital and Spaulding Rehabilitation Hospital (85% of all 1325 ischemic stroke patients given broad inclusion criteria). It is expected that ~20% of the patients will agree to participate based on prior experience of recruitment in this population. This creates a pool of 225 or 19 per month. Thus, the study team can feasibly recruit 60 patients within 4-5 months with buffer for unexpected issues.

Assuming a mean blood pressure of 150 +/- 13 points in the individual counselling arm and an alpha of 0.05, this study will need to enroll a total of 54 patients (i.e., 27 per arm) to have 80% power to detect a 10 mm Hg reduction blood pressure from the social network intervention. Therefore, planned enrollment of 60 should be sufficient power for this study to allow for loss to follow-up.

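### Spaulding enrols but has no stated randomisation stratum, and section 9.3 does not prespecify the stratification factors as covariates; the cost is precision, not validity

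*Combined protocol and SAP*

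**What the plan says.** Three hospitals supply patients. Section 3 (General Description of Study Design) says: "The study will enroll 60 patients hospitalized at Brigham and Women's Hospital, Massachusetts General Hospital and Spaulding Rehabilitation Hospital". Section 4.1a repeats the list. Section 4.2a has staff screen daily at Brigham and Women's, "Massachusetts General Hospital and Spaulding Rehabilitation Hospital inpatient admissions based on the study's inclusion and exclusion criteria". Section 9.2 counts all three in the forecast: "the study team expects 1126 patients to be eligible across Brigham and Women's Hospital, Massachusetts General Hospital and Spaulding Rehabilitation Hospital".

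The allocation is described twice. Section 5.1 stratifies by network size (under 5, or 5 and more) and by "location of hospitalization (MGH or BWH), and then be randomized using a 1:1 ratio". Section 3 gives the same two factors with the same two locations. Neither section assigns Spaulding patients to a level.

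For the analysis, section 9.3 specifies a linear model for the primary outcome and for physical function, "controlling for any differences in baseline variables despite randomization". The logistic model for reaching the blood pressure goal follows the same rule. Network size and location are not named in section 9.3, and no list of covariates or threshold for a difference is given.

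**The concern.** There are two linked gaps.

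First, the location factor has fewer levels than there are enrolling hospitals. Read literally, the rule gives a Spaulding inpatient no level, and the text offers no convention to settle it. An analyst could not reconstruct from the documents which stratum such a patient belonged to.

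Second, the covariate rule works against the stratification. A factor enters the model only if the arms differ on it, and stratified allocation is meant to prevent that difference. The factors judged important enough to stratify on are therefore among the least likely to be adjusted for. Section 3 justifies network size by its relation to stroke recovery, which bears directly on the physical function outcome.

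What is at stake is efficiency in a small trial with little slack, and an analysis whose covariates depend on what the data show.

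**Working it through.** **Inputs.** From section 9.2: difference 10 mm Hg, SD 13 mm Hg, alpha 0.05, power 80%, 27 per arm (54 in total), 60 planned. Two-sided testing is assumed because it reproduces the stated size. The SD is taken to apply to the outcome analysed. The share of variance explained by the strata, R², is not in the documents; 0 to 30% is used as an assumed range.

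**Step 1: the plan's own figure.** n per arm = 2 × (1.960 + 0.842)² × 13² / 10² = 26.5, so 27 per arm and 54 in total. This matches. Power is 80.7% at 27 per arm and 84.6% at 30 by the normal approximation, or 79.2% and 83.4% with the t distribution. The stratum question does not change the sample size.

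**Step 2: why omission is conservative.** If allocation balances the strata, the between-strata variance drops out of the treatment difference. The true variance of the difference is about (1 − R²) × 2 × 13² / n. An unadjusted test still estimates it as 2 × 13² / n, so its standard error is too large by 1/√(1 − R²).

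- R² = 10%: factor 1.054; type I error = 2 × [1 − Φ(1.96 × 1.054)] = 0.039.
- R² = 20%: factor 1.118; type I error = 2 × [1 − Φ(1.96 × 1.118)] = 0.028.

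**Step 3: power at 27 per arm, normal approximation.** The unadjusted standard error is 13 × √(2/27) = 3.54, so the standardised effect is 10/3.54 = 2.826. The unadjusted test under stratified allocation has power Φ[(2.826 − 1.96)/√(1 − R²)]. The adjusted test has power Φ[2.826/√(1 − R²) − 1.96].

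| Assumed R² | Unadjusted | Adjusted | Gain |
|---|---|---|---|
| 0 | 80.7% | 80.7% | 0 |
| 10% | 81.9% | 84.6% | 2.7 points |
| 20% | 83.4% | 88.5% | 5.1 points |

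Simulation at 27 per arm gives about 81% to 84% at R² = 10% and 82% to 88% at 20%, a gain of about 3 to 6 points. The unadjusted test also benefits from stratified allocation, so comparing the adjusted power with the plain 79% would overstate the gain.

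**Step 4: simulation at the planned 60 patients.** Settings: blocks of 4 (assumed; the documents give no block size), equally likely cells, total SD 13, 4,000 runs per setting. Entries are unadjusted / adjusted.

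| Assumed R² | Type I error, 4 cells | Power, 4 cells | Type I error, 6 cells | Power, 6 cells |
|---|---|---|---|---|
| 0 | 0.047 / 0.046 | 0.833 / 0.833 | 0.051 / 0.052 | 0.829 / 0.824 |
| 10% | 0.035 / 0.045 | 0.856 / 0.873 | 0.043 / 0.051 | 0.844 / 0.867 |
| 20% | 0.031 / 0.052 | 0.861 / 0.906 | 0.029 / 0.050 | 0.855 / 0.904 |
| 30% | 0.023 / 0.049 | 0.876 / 0.938 | 0.021 / 0.051 | 0.867 / 0.936 |

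The unadjusted test is never materially above 0.05, and the adjusted test stays near it. If the strata explain nothing, adjustment costs less than 1 point. These figures concern the linear model for systolic pressure; the logistic model was not simulated.

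**The case against.** A reader might infer three stronger conclusions. The documents support none of them.

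*Spaulding patients cannot be stratified.* Section 3 maps networks during the index stroke admission and then stratifies by location of hospitalisation, and section 4.1a limits enrolment to "Within 14 days after stroke". Location could therefore mean the acute hospital, which would give many Spaulding patients a level. That reading is stated nowhere, and it fails for a patient whose acute stay was at neither hospital. What the text shows is an unstated rule; it does not show that patients lack a stratum in practice or that staff choose one ad hoc.

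*The stratified design is not used.* It is used, in allocation. Nor does section 9.3 exclude network size or location: either could enter if it differed at baseline. The accurate statement is that they are not prespecified.

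*The comparison is biased or the test invalid.* Omitting balanced strata makes the test conservative, as shown above. Poor balance among Spaulding patients would be a chance event with expectation zero. As an illustration with assumed figures, suppose 12 of 60 patients come from Spaulding, split 8 to 4, and differ by 10 mm Hg. The treatment difference then moves by 10 × (8 − 4)/30 = 1.3 mm Hg in that one unfavourable draw. The documents give neither the Spaulding share nor such a difference.

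It is also fair to say that section 3 links network size to stroke recovery, not to blood pressure, so the gain for the primary outcome could be near zero. That limits the size of the benefit. It does not remove the inconsistency in the location levels or the weakness of the covariate rule.

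**Conclusion.** The point holds in a limited form. The location factor in sections 3 and 5.1 does not match the list of enrolling hospitals, and section 9.3 leaves out the factors used to randomise unless chance brings them in. The expected harm is efficiency: a gain of about 3 to 6 points of power at 27 per arm is forgone if the strata explain 10% to 20% of variance, against a cost of at most about 1 point if they explain none. That range rests on an assumed R² and on reasonably balanced allocation within strata. The sample size stands, and nothing here shows bias or excess false positives. This is a free improvement to the analysis plus a clarification of the allocation rule.

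**What to change.** **Section 9.3.** Prespecify network-size stratum and the location factor, coded exactly as used in randomisation, as main-effect covariates in the linear and logistic models, whether or not they differ at baseline. Name any further baseline covariates in advance, for example baseline systolic pressure, age or stroke severity, all of which the data collection schedule already includes. Replacing the present rule with the two stratification factors alone would close the only route by which those variables can enter, so the list should be settled at the same time.

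**Sections 3 and 5.1.** State how Spaulding patients are stratified: as a third location level, or by the hospital of the acute admission. If by acute hospital, also cover patients whose acute stay was elsewhere, and use that same coding in the model rather than the enrolling site.

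**If randomisation has begun.** Document the rule actually applied and analyse by it; do not change the allocation scheme. The documents do not give recruitment status.

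**Cost.** A few sentences, with no added patients or data. A third level raises the cells from 4 (average 60/4 = 15 patients) to 6 (average 60/6 = 10). That is workable with main effects only, though sparser cells make exact balance within each one harder to achieve.
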